1 LIST OF ABBREVIATIONS

[figure not shown]
	List in alphabetical order
ADHD	Attention-Deficit Hyperactivity Disorder
AE	Adverse Event
API	Attention Performance Index
CFR	Code of Federal Regulations
CPT	Continuous Performance Test
CRF	Case Report Form
eCRF	Electronic Case Report Form
EEG	Electroencephalography
FDA	Food and Drug Administration
FDAAA	Food and Drug Administration Amendments Act of 2007
GCP	Good Clinical Practice
GMP	Good Manufacturing Practices
HIPAA	Health Insurance Portability and Accountability Act
ICF	Informed Consent Form
ICH	International Conference on Harmonization
ICMJE	International Committee of Medical Journal Editors
IDE	Investigational Device Exemption
IND	Investigational New Drug Application
IRB	Institutional Review Board
MedDRA	Medical Dictionary for Regulatory Activities
NCT	National Clinical Trial
NT	Neurotypical
PI	Principle Investigator
SAE	Serious Adverse Event
SAP	Statistical Analysis Plan
SOA	Schedule of Activities
TOVA	Test of Variables of Attention

1 PROTOCOL SUMMARY

1.1 SYNOPSIS

Title:	A study to assess Midline Frontal Theta (MFT) power as measured by stimulus-locked electroencephalography (EEG) before and after AKL-T01 treatment for improving attention in pediatric participants ages 8-12 years old with Attention Deficit Hyperactivity Disorder (ADHD)
Hypothesis:	ADHD children receiving 4 weeks of AKL-T01 treatment will show enhancement in MFT activity as measured by stimulus-locked EEG.
Objectives:	
Primary Objective:
 
• Demonstrate enhancement of MFT power measured by stimulus-locked EEG (Perceptual Discrimination Task (PDT)=Stimulus) in children with ADHD following 4 weeks of at-home AKL-T01 treatment. 
Secondary Objective:
 
• Demonstrate normalized MFT power in children with ADHD following 4 weeks of at-home AKL-T01 treatment. 
Exploratory Objectives:
 
• Demonstrate improvement in sustained attention by direct assessment in children with ADHD following 4 weeks of at-home AKL-T01 treatment.• Demonstrate improvement in ADHD symptoms by parent report in children with ADHD following 4 weeks of at-home AKL-T01 treatment.
Endpoints:	
Primary Endpoint:
 
• PDT-locked EEG relative to pre-training 
Secondary Endpoint:
 
• PDT-locked EEG relative to a normative control cohort 
Exploratory Endpoints:
 
• Project EVO Assessment• Test of Variables of Attention (TOVA)• Vanderbilt Assessment
Study Population:	30 children ages 8 to 12 with ADHD from the United States
Description of Study Intervention:	AKL-T01 is a digital therapeutic software for the treatment of attention and inhibitory control deficits in patients with ADHD. AKL-T01 is an investigational medical device known as Software as a Medical Device (SaMD).
Study Duration:	From beginning of enrollment to last subject last visit, 12 months
Participant Duration:	29 Days

1.2 SCHEMA

1.3 SCHEDULE OF ACTIVITIES (SOA)

Procedures	Screening* Day -7 to -3 (Participants washing out stimulants only)	Enrollment / Baseline* Day 0	Treatment Days 1 to 27	Follow Up Day 28 +3 days
Parent Informed consent		X		
Child Assent		X		
Mini-International Neuropsychiatric Interview for Children and Adolescents (MINI-KID)		X		
Demographics	X			
Medical history	X			
Wechsler Intelligence Scale for Children V (WISC V)		X		
Ishihara Colorblindness Test		X		
Vanderbilt ADHD Diagnostic Parent Rating Scale (Initial and Follow-Up)		X		X
Social Communication Questionnaire		X		
Short Sensory Profile		X		
Social Competence Scale		X		X
Video Game Play Questionnaire		X		
Behavior Assessment for Children, Second Edition (BASC-2)		X		
Beery Visual Motor Integration (VMI)		X		
Adaptive Cognitive Evaluation (ACE) [†]		X		X
Neuroracer [†] -locked EEG		X		X
Resting State EEG		X		X
AKL-M01 (AKL-T01 Monitor) [†]		X		X
Test of Variables of Attention (TOVA) [†]		X		X
Basic Response Time (BRT)		X		X
Administer AKL-T01		X		
AKL-T01 Compliance Monitoring			X	
Adverse Event (AE) Assessment				X
Complete Case Report Forms (CRFs)	X	X	X	X

* Screening and Baseline visits may be a combined visit for participants not washing out stimulant medication.

[†] Interventions are computerized

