4 STUDY DESIGN

4.1 OVERALL DESIGN

This study is a single arm, open-label, pilot study to assess midline frontal theta (MFT) power as measured by stimulus-locked electroencephalogram (EEG) before and after treatment with AKL-T01 for improving attention in pediatric participants ages 8-12 years old with attention deficit hyperactivity disorder (ADHD).

All participants enrolled in this study will not be taking ADHD medications, including stimulants, for the duration of the study. Participants who are taking ADHD medications prior to Day 0 must have been stable off of medications for at least 30 days per parent report, or washout of medications at a Screening visit 3 – 7 days prior to Day 0.

At Baseline / Day 0, all eligible participants will complete both resting-state and PDT-locked EEG, as well as the TOVA, Vanderbilt, and AKL-M01 assessments.

All participants will then play AKL-T01 for approximately 25 minutes per day, 5 days per week, for 4 weeks at home.

At Follow-up / Day 28, participants will repeat both resting-state and PDT-locked EEG, as well as the TOVA, Vanderbilt, and AKL-M01 assessments.

All study visits for each participant should be completed during the same time of day (either AM or PM), to maintain consistent data collection and comparison of rater assessment results.

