5 STUDY POPULATION

5.1 INCLUSION CRITERIA

In order to be eligible to participate in this study, an individual must meet all of the following criteria:

1. Age 8 to 12 at the time of parental informed consent
2. Male or female
3. Confirmed ADHD diagnosis at screening/baseline visit based on DSM-V criteria and established via the MINI-KID administered by a trained clinician either in person or via teleconference
4. WISC V FSIQ ≥ 70
5. Vanderbilt ADHD Diagnostic Parent Rating Scale: Must score a 2 or 3 on at least 6 items 1-9 AND must score a 4 on at least 2, or 5 on at least 1, of items 48-54 (performance questions).
6. Consistently off stimulant medication for ≥ 1 week. OR currently on stimulant medication and agree to stop taking the medication for a 1 week prior to the baseline visit and off through duration of training and post-training assessment (note: participants will only be allowed to washout of stimulant medication if in the opinion of the investigator they are currently inadequately managed on their medication and it is appropriate to stop taking their medication for the duration of the trial)
7. Consistently off Psychotropic drug for ≥ 1 month
8. Consistently off non-stimulant medication for ADHD (e.g. atomoxetine, clonidine, guanfacine) for ≥ 1 month

9. Able to follow written and verbal instructions (English) as assessed by the PI and/or study coordinator
10. Functioning at an age-appropriate level intellectually
11. Able to comply with all testing and requirements

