5.2 EXCLUSION CRITERIA

An individual who meets any of the following criteria will be excluded from participation in this study:

1. Current controlled (requiring a restricted medication) or uncontrolled, comorbid psychiatric diagnosis, based on the Neurodevelopment Intake Form, BASC, and subsequent clinical interviewing, with significant symptoms including but not limited to post-traumatic stress disorder, psychosis, bipolar illness, severe obsessive compulsive disorder, severe depressive or anxiety disorder, conduct disorder, or other symptomatic manifestations that in the opinion of the Investigator may confound study data/assessments. (Participants with clinical history of learning disorders will be allowed to participate as long as the disorder does not impact their ability to participate based on PI judgement).
2. Autism Spectrum Disorder concern as indicated from the Social Communication Questionnaire ≥ 15 .
3. Current treatment with stimulant treatment for ADHD and unwilling or inappropriate (per investigator opinion) to washout.
4. Initiation or completion of behavioral therapy within the last 4 weeks. The participant should inform the Investigator if they intend to change their behavioral therapy during the 4 weeks of the study. Participants who have been in behavior therapy consistently for more than 4 weeks may participate if their routine is unchanged throughout the study.
5. Participant is currently considered at risk for attempting suicide by the Investigator, has previously made a suicide attempt, or has a prior history of, or is currently demonstrating active suicidal ideation or self-injurious behavior, as measured by MINI-KID Suicidality Module C.
6. Motor condition (e.g. physical deformity of the hands/arms) that prevents game playing as reported by the parent or observed by the Investigator.
7. Recent history or suspicion (within the past 6 months) of substance abuse or dependence.
8. History of seizures (excluding febrile seizures).
9. Participation in a clinical trial within 90 days prior to screening.
10. Color blindness as detected by Ishihara Color Blindness Test.
11. Regular use of psychoactive drugs that in the opinion of the Investigator may confound study data/assessments.
12. Any other medical condition that in the opinion of the Investigator may confound study data/assessments.
13. Previously received AKL-T01 (Project-EVO™) treatment in a previous clinical trial.

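### For children washing out stimulants, the Schedule first marks consent, assent and the structured eligibility tests at Day 0, after medication has already been stopped for the trial

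*Combined protocol and SAP*

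**What the plan says.** Section 1.3 heads its first column Screening, "Day -7 to -3 (Participants washing out stimulants only"). That column has three marks: demographics, medical history and case report forms. The rows for parent consent, child assent, MINI-KID, WISC V, Ishihara, Vanderbilt, SCQ and BASC-2 are blank there and first marked under Enrollment / Baseline, Day 0. The footnote says "Screening and Baseline visits may be a combined visit for participants not washing out stimulant medication", so it does not merge the two visits for children who are washing out.

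Two places say when stimulants stop:
- Section 4.1: "washout of medications at a Screening visit 3 – 7 days prior to Day 0".
- Section 5.1, inclusion 6: the family must "agree to stop taking the medication for a 1 week prior to the baseline visit" and the child stays off through the post-training assessment. Washout is open only to children for whom the investigator considers that "they are currently inadequately managed on their medication and it is appropriate to stop taking their medication" for the length of the trial.

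Three other criteria bear on timing:
- Inclusion 3 asks for a "Confirmed ADHD diagnosis at screening/baseline visit" and allows the MINI-KID by teleconference.
- Exclusion 3 removes children on stimulants who are unwilling to wash out, or for whom the investigator thinks it inappropriate.
- Exclusion 5 begins with a child "currently considered at risk for attempting suicide by the Investigator", a judgement that need not wait for a test, and then refers to Module C of the MINI-KID.

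**The concern.** The washout is done for the trial, in children aged 8 to 12. In the Schedule's order, a washout child attends Screening, gives demographic and medical history data, stops stimulants, and only at the next visit reaches the consent and assent marks. Inclusion 6 needs the family's agreement before baseline, but nothing in the text available places written consent or assent ahead of that step.

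The same order means a child can stop treatment and then fail a test that has no bearing on medication status, such as colour vision. That child has gone without ADHD medication for a trial the child cannot join. Section 8.1 gives the MINI-KID the job of confirming ADHD and finding excluding comorbidity. Its result would help the investigator decide whether stopping is worthwhile, yet the Schedule marks it after the decision.

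**Working it through.** No sample-size or error-rate figure is involved. The check compares the Schedule with sections 4.1, 5.1, 5.2 and 8.1.

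**1. Are the Schedule's columns readable?** Case report forms are marked in all four columns, compliance monitoring in the third and adverse events in the fourth. The columns therefore appear intact, and the blank Screening cells can be taken as blank.

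**2. What is marked before washout?** Consent and assent: 0 of 2 at Screening, 2 of 2 at Day 0. Structured tests named in sections 5.1 and 5.2 (MINI-KID, WISC V, Vanderbilt, BASC-2, SCQ, Ishihara): 0 of 6 at Screening, 6 of 6 at Day 0.

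**3. How long is the child off medication by then?** 3 to 7 days under section 4.1, or at least 7 days under inclusion 6. Both put the stop before Day 0. The two agree only if Screening falls on Day -7. The window Day -7 to -3 has 5 days, so a strict 1-week rule rules out Days -6, -5, -4 and -3, which is 4 of 5.

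**4. Which criteria rest, wholly or partly, on a test first marked at Day 0?** Seven do:

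| Criterion | Test | Already possible before washout? | After the fix |
|---|---|---|---|
| Inclusion 3 | MINI-KID | Yes, the criterion allows Screening or teleconference | Made explicit before washout |
| Inclusion 4 | WISC V | Not scheduled | May still be decided after washout |
| Inclusion 5 | Vanderbilt | Not scheduled | May still be decided after washout |
| Exclusion 1 | BASC, with intake form, interview and investigator opinion | In part, from history | May still be decided after washout |
| Exclusion 2 | SCQ of 15 or more | Not scheduled | Newly settled before washout |
| Exclusion 5 | Module C, plus investigator's judgement | Yes, if the MINI-KID is done early | Module C part made explicit before washout |
| Exclusion 10 | Ishihara | Not scheduled | Newly settled before washout |

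So 2 are newly settled, 2 are made explicit and 3 remain: 2 + 2 + 3 = 7. Inclusion 10 (age-appropriate intellectual level) may also draw on the WISC V, but it names no test and is not counted.

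**5. What moves, in minutes?** Times are from section 8.1, taking its PDT-locked EEG to be the Schedule's Neuroracer-locked EEG. Timed Day 0 load: MINI-KID 20 + WISC V 60 + Ishihara 5 + Vanderbilt 20 + resting EEG 6 + PDT-locked EEG 60 + TOVA 22 + AKL-M01 20 = 213 minutes.
- Moving Ishihara: 5 minutes to Screening; Day 0 becomes 213 - 5 = 208.
- Moving Ishihara and MINI-KID: 5 + 20 = 25 minutes to Screening; Day 0 becomes 213 - 25 = 188.
- The SCQ and the consent discussion have no stated time.

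**The case against.** **The Schedule may simply be loosely drawn.** Demographics and medical history are marked only in the washout-only column, so a literal reading would leave the other children with no history at all. The protocol also commits to ICH GCP and 21 CFR Part 50. This has force. A reader might infer that the sponsor planned to withdraw medication without consent, or that sites did so. The documents do not support that: the consent form is not in the text reviewed, and a misplaced mark explains the Schedule equally well. But a general commitment does not correct the table that sites follow.

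**The protocol already protects these children.** Inclusion 6 and exclusion 3 both require the investigator to judge washout appropriate, medical history is taken at Screening, and exclusion 5 starts with the investigator's own view of suicide risk. These safeguards stand and narrow the harm. They do not supply consent, and they do not detect unrecognised colour blindness or an SCQ of 15 or more ("Autism Spectrum Disorder concern as indicated from the Social Communication Questionnaire").

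**The MINI-KID can already be done at Screening.** Correct. Inclusion 3 does not conflict with the Schedule, and it cannot be said that the investigator necessarily decides without the result. What is missing is an instruction to use that option.

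**Test timing is a preference.** In part. Testing every child off medication is defensible, and this is why WISC V, BASC-2 and Vanderbilt are left alone. The argument does not reach consent, assent or Ishihara.

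**More could be moved.** A reader might infer that moving WISC V and BASC-2 as well would settle all but the Vanderbilt criterion. It would not: exclusion 1 also needs the Neurodevelopment Intake Form, which has no Schedule row, together with interviewing and investigator opinion.

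**Conclusion.** The point holds for the Schedule. For washout children it places documented consent, assent and all six structured eligibility tests after a trial-driven stop of medication, by 3 to 7 days or by 1 week depending on which section governs. It also places demographic and history collection before the marked consent. The amendment should be made.

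The size in children cannot be derived. Planned enrolment is 30, but the documents give neither the share washing out nor a Day 0 failure rate. Only failures not already recognised from history count, and washout is limited to children judged inadequately managed.

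Two further inferences are not supported. Nothing here shows bias in midline frontal theta power or any other endpoint, since every efficacy baseline is at Day 0 in any case. And although exclusion 5 is involved, the documents do not say that stopping stimulants raises suicide risk.

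The conclusion assumes that the Schedule's columns were extracted correctly and that sites would follow it as written. If sites already take consent at Screening, the amendment only records that.

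**What to change.** For washout children only, amend section 1.3 and align the text:

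1. Mark parent consent and child assent at Screening, before any procedure or washout.
2. Mark Ishihara and SCQ at Screening.
3. Use the option inclusion 3 already gives: do the MINI-KID, with Module C, at Screening or by teleconference, after consent and before the investigator's washout decision.
4. State that stimulants stop only after consent and these checks.
5. Use one washout length in section 4.1, inclusion 6 and the Screening window. With 3 to 7 days, the window stands. With 1 week, Screening falls on Day -7 or earlier, and 4 of the 5 current days are lost unless the window is extended backwards.

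Leave WISC V, BASC-2, Vanderbilt and all efficacy baselines at Day 0. Moving WISC V or BASC-2 is for the sponsor to choose. Nothing changes for children not washing out, and the decision to stop medication stays with the investigator.

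**Cost.** No test or visit is added. Screening grows by 5 timed minutes, or 25 with the MINI-KID, plus the SCQ and consent discussion, and Day 0 shortens by the same timed amount. Some children would take the MINI-KID on medication while others take it off. Inclusions 4 and 5 and exclusion 1 may still be decided after washout.

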6.1.2 STUDY INTERVENTION COMPLIANCE

AKL-T01 automatically captures gameplay compliance and uploads these data directly to a central server when connected to WiFi. The server will automatically push daily compliance emails to the research coordinator. Based on these emails study staff can then reach out to parents and caregivers of participants to trouble shoot technical problems and/or encourage more play.

Additionally, AKL-T01 contains built-in features that remind the participant to play each day.

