8.3.5 TIME PERIOD AND FREQUENCY FOR EVENT ASSESSMENT AND FOLLOW-UP

The occurrence of an ADE may come to the attention of study personnel during study visits and interviews of a study participant presenting for medical care, or upon review by a study monitor.

Information to be collected includes event description, time of onset, clinician's assessment of severity, relationship to study product (assessed only by those with the training and authority to make a diagnosis), and time of resolution/stabilization of the event. All ADEs occurring while on study will be documented appropriately regardless of relationship. All ADEs will be followed to adequate resolution.

Any medical condition that is present at the time that the participant is screened will be considered as baseline and not reported as an ADE. However, if the study participant's condition deteriorates at any time during the study, it will be recorded as an ADE.

Changes in the severity of an ADE will be documented to allow an assessment of the duration of the event at each level of severity to be performed. ADEs characterized as intermittent require documentation of onset and duration of each episode.

The Site Principal Investigator will record all reportable events with start dates occurring from the time of enrollment through the final study visit. At each study visit, the investigator will inquire about the occurrence of ADEs since the last visit. Events will be followed for outcome information until resolution or stabilization.

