8.3.6 ADVERSE EVENT REPORTING

It is understood that complete information about an event may not be known at the time the initial report is submitted. The investigator must assess the relationship of the event to the investigational device (including rationale for assessment) and should make every attempt to obtain as much information as possible concerning the event. Additional information pertaining to an event should be reported in the case report form as it becomes available.

The investigator must report all adverse device effects (anticipated or unanticipated) occurring from the time of enrollment through the final study visit within 24 hours of knowledge of the event.

The investigator must report when important follow-up information (final diagnosis, outcome, results of specific investigations, etc.) becomes available after submission of the initial ADE form and information. Follow-up information should be submitted according to the same process used for reporting the initial event as described above (i.e., within 24 hours of knowledge, via <specify method>). All adverse device effects will be followed through resolution.

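### The Schedule has one adverse event enquiry, at Day 28 (+3): it conflicts with Section 8.3.5, leaves episode-level data to about a month of recall, and can miss events that resolve before an early exit

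*Combined protocol and SAP*

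**What the plan says.** The Schedule (1.3) lists "Adverse Event (AE) Assessment" with one mark, in the column headed "Follow Up Day 28 +3 days". The Day 0 column, where AKL-T01 is administered, is blank in that row. So is the column headed "Treatment Days 1 to 27", where only compliance monitoring and case report forms are marked.

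Section 4.1 places the treatment at home: "All participants will then play AKL-T01 for approximately 25 minutes per day, 5 days per week, for 4 weeks at home".

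Section 8.3.5 sets a fuller standard. It states: "At each study visit, the investigator will inquire about the occurrence of ADEs since the last visit". It also states: "ADEs characterized as intermittent require documentation of onset and duration of each episode". Changes in severity are to be documented so that time spent at each level can be assessed. Besides visits, it names two ways an ADE may surface: the child presents for medical care, or a monitor finds it on review. Section 8.3.6 requires reports "within 24 hours of knowledge of the event".

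Section 6.1.2 gives staff daily compliance emails and says they can then contact families to "trouble shoot technical problems and/or encourage more play". Section 7.1.1 requires adverse experiences present at discontinuation or withdrawal to be reported and followed up. Section 7.1.2 requires efforts to regain contact and reschedule a missed Day 28 visit.

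**The concern.** Section 8.2 names the evaluation of ADEs as the content of the safety assessment, so the enquiry about them is nearly all of the active safety follow-up. The plan asks for episode-level detail but schedules no occasion or tool to collect it while the device is in use.

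Two things are at stake. The first is data quality: dates, durations and severity changes reconstructed a month later are less reliable than those recorded near the event. The second is completeness. Mild effects that have passed may be forgotten by Day 28, and a child who leaves early may never be asked about effects that have already resolved. Both errors lower the ADE count. The study has a single arm, so no comparison group shares the same loss, and the under-count carries straight into any description of tolerability.

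The compliance contacts matter because falling play may itself signal a problem. Section 2.3.1 accepts that a frustrated or fatigued child may stop, and 8.3.3 lists reduced tolerance of frustration as an expected device effect. Yet 6.1.2 does not tell staff to ask why play fell.

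**Working it through.** The plan states no figure to reproduce here. The check sets the sections side by side and adds simple arithmetic.

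**1. Enquiries by visit**

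| Time | Schedule (1.3) | Section 8.3.5 |
|---|---|---|
| Day 0 (AKL-T01 administered) | no mark | enquiry required |
| Days 1 to 27 | no mark | no visit, so no enquiry |
| Day 28 (+3) | mark | enquiry required |

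The two sections disagree at Day 0. An ADE is by definition related to device use, so a Day 0 enquiry is informative only if made after first use. For Days 1 to 27 both sections give no scheduled enquiry.

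**2. Recall interval**

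Inputs: device administered at Day 0; follow-up at Day 28, window +3 days (both from 1.3).

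- Shortest: 28 − 0 = 28 days.
- Longest: (28 + 3) − 0 = 31 days.
- If first play is on Day 1 rather than Day 0, each figure falls by one day, to 27 and 30.

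**3. Exposure covered by that one enquiry**

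Inputs from 4.1: 5 days per week for 4 weeks. 5 × 4 = 20 prescribed play days.

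**4. What is captured when a child leaves early**

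| Event | Capture stated in the plan |
|---|---|
| Present at withdrawal | yes (7.1.1) |
| Reason for discontinuing | yes, with immediate notice to the sponsor (7.1.1) |
| Resolved before withdrawal | no enquiry specified |
| Child misses Day 28, later rescheduled | yes, at the rescheduled visit (7.1.2) |
| Child lost to follow-up | no enquiry specified beyond attempts at contact (7.1.2) |

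**5. How many children this could touch**

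Input: 30 planned participants (1.1). The documents give no dropout rate, so the early-exit share is an assumption.

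- At 5%: 30 × 0.05 = 1.5 children.
- At 20%: 30 × 0.20 = 6 children.

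These children miss the scheduled Day 28 enquiry. Not all of them would have had an ADE, and some ADEs would still be caught under 7.1.1 or by the passive routes. No expected ADE rate is given, so the number of missed events cannot be calculated.

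**The case against.** The strongest reply is that this is a 30-child pilot of software. Section 2.3.1 calls the risks very small and 2.3.3 reports no serious adverse events to date. No objective, endpoint or analysis estimates an ADE rate, and 9.2 defines no safety population. Nothing in the documents requires enquiry between visits. Events can surface through medical care or monitor review, and 8.3.5 requires all reportable events from enrollment to the final visit to be recorded. Case report forms are marked during the treatment period, and their content is not in the documents.

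Much of this stands as a limit on the point, and it rules out several stronger readings that a reader might infer:

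- *The 24-hour rule cannot be met.* Not supported. The clock in 8.3.6 runs from knowledge, so an event first heard of at Day 28 can be reported on time. Late enquiry delays knowledge but does not break the rule.
- *Episode data cannot be collected.* Too strong. They can be collected by recall, with less precision. The documents also do not say whether the listed effects are brief or recurrent.
- *Early leavers have no capture at all.* Section 7.1.1 covers events present at withdrawal and discontinuations because of an adverse experience. The gap is resolved events and children lost to follow-up.
- *Home use is unmonitored, or staff will press symptomatic children to play.* Play is monitored remotely for compliance. Section 6.1.2 does not forbid a safety question; it simply does not ask for one.

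The reply does not remove the conflict at Day 0. Nor does it explain how the episode and severity-duration data, which the plan itself requires, are to be obtained reliably. The routes it relies on are passive and suit events that lead to medical care better than mild ones. A form marked in the Schedule does not show that anyone asks the family.

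**Conclusion.** The point holds in limited form. The Schedule and 8.3.5 contradict each other at Day 0. Under either, there is one scheduled enquiry after home treatment begins, 28 to 31 days after Day 0 and covering about 20 play days. The detail required by 8.3.5 therefore depends mainly on recall. Resolved events in children who withdraw, and events in those lost to follow-up, can go unrecorded. On an assumed early-exit share of 5% to 20%, about 1.5 to 6 of 30 children would miss the scheduled enquiry; the range is illustrative.

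The likely direction is too few ADEs counted, and so a device that looks better tolerated than it is. The size of that bias cannot be estimated from the documents. The EEG comparison is not affected. This is an inexpensive improvement that should be made, not a defect that invalidates the study.

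**What to change.** - **Schedule (1.3):** reconcile the AE row with 8.3.5. Mark it at Day 0 (after first use) and Day 28, and in the Treatment column for staff contacts.
- **Section 6.1.2:** at each compliance contact, have staff ask why play was missed and whether any adverse effect occurred, with onset, duration and severity, and record the answer under 8.3.
- **Sections 7.1.1 and 7.1.2:** at the withdrawal or last-contact call, ask about all ADEs since the last visit, including those that have resolved. A child who cannot be reached remains a gap, and the number of such children should be reported.
- **Optional:** put a brief periodic question to all families by the same route. Without it, mid-treatment enquiry reaches mainly families whose child plays less, so detection would depend on adherence. The frequency is a design preference; the documents do not dictate one.

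The cost is one Schedule row, short additions to three sections and a brief script for the coordinator. In use it takes a few minutes per contact. More mild ADEs will be counted, and the report should say that the count reflects active enquiry.
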